1.1 Background and rationale

Adequate maternal nutrition is important for maternal health and wellness and is a major determinant of pregnancy outcomes [1]. In low-and middle-income countries (LMICs), maternal and child malnutrition is a public health concern resulting in increases of morbidity and mortality [2]. Poor maternal nutrition is associated with adverse pregnancy outcomes such as low birth weight (LBW), preterm birth, large- and small-for-gestational age, intrauterine growth restriction, cesarean delivery and gestational diabetes mellitus [1, 2]. In the long term, maternal undernutrition is associated with chronic diseases (e.g., glucose intolerance, coronary heart disease, obesity, and increased risk of breast cancer), less schooling and reduced economic productivity in offspring exposed to undernutrition during fetal life [1-3].

Routine antenatal care (ANC) offers opportunities to receive a broad range of health promotion and prevention services including support for adequate nutritional care for pregnant women and their newborns, and any required medical treatment [4]. However, it has been shown that in LMICs half of women did not receive the four ANC visits (recommended until 2016) and the quality of ANC was suboptimal for those who met the recommendation [5, 6]. In 2016, World Health Organization (WHO) updated its guidelines on ANC with a high priority placed on nutrition interventions. These new guidelines recommended increasing the number of ANC from four to at least eight contacts to improve women's positive experience of care and to reduce perinatal morbidity and mortality [7]. Following these new recommendations, the government of Burkina Faso is working with WHO and other partners to revise the national guidelines on ANC and eventually test elements of the essential core package of routine ANC needed by women throughout pregnancy.

In Burkina Faso, despite continued improvement, the adjusted maternal mortality ratio (371 deaths per 100,000 live births) [8] and the neonatal mortality rate (25 deaths per 1,000 live births) remain high [9]. Anemia and severe acute malnutrition are among the ten principal causes of death among children under five years, in health facilities [10]. According to the findings from the 2017 Performance Monitoring and Accountability (PMA) 2020 nutrition survey, among women age 10-49 years who had a live birth in the last two years, 83% visited a qualified ANC provider. Among those who sought prenatal care, 70% of women reported attending at least four visits [11]. However, information on nutritional status shows that undernutrition is highly prevalent among women and children. According to the 2010 DHS, 16% of women of child-bearing age were undernourished (BMI <18.5kg/m²), and 58% of pregnant women were anemic [12]. There is still a high prevalence of LBW (14%) and stunting among under five years of age (33%) [8]. All this suggests the need to reinforce nutrition interventions provided during pregnancy and enhance coverage and utilization of ANC services.

Alive and Thrive (A&T) is an initiative that supports the scaling up of nutrition interventions to save lives, prevent illnesses, and contribute to healthy growth and development through improved maternal nutrition, breastfeeding and complementary feeding practices in several countries. Since 2014, A&T has worked with the Burkina Faso Ministry of Health (MOH) to scale up breastfeeding nationally and is now working to support the MOH and various international and local partners to scale up interventions to address a full range of maternal, infant, and young child nutrition (MIYCN) practices.

In Burkina Faso, A&T will develop and test the integration of an intensive package of maternal nutrition interventions into existing ANC services delivered through government health facilities that will align with the latest global evidence [7]. These include intensified counseling and support on dietary diversity and quality during pregnancy, iron-folic acid (IFA) supplements consumption, importance of ANC and increasing the number of visits, adequate weight-gain monitoring, and early initiation of and exclusive breastfeeding. The International Food Policy Research Institute (IFPRI) will carry out a research study to assess the feasibility of integrating this package of maternal interventions into existing ANC services and to identify enabling factors and challenges. The findings of this evaluation study will provide the MOH and its partners with important information needed to scale up interventions to achieve the new ANC recommendations.

1.2 Objectives

The overall study objective is to evaluate the feasibility and impact of integrating locally relevant maternal nutrition interventions into existing ANC services on diet quality and utilization of nutrition interventions during pregnancy.

[figure not shown]
Research questions for the evaluation include:

- 1) Is it **feasible** to integrate locally relevant maternal nutrition interventions based on the WHO ANC guidelines into existing ANC services delivered through government health facilities?
- 2) Can the **coverage and utilization** of key nutrition interventions (nutrition counseling, weight gain monitoring, IFA supplement consumption) be improved by integrating nutrition-focused social and behavior change communication (SBCC; community mobilization and interpersonal communication) and systems strengthening approaches into existing ANC services?
- 3) Can the **quality of diets** (dietary diversity and adequate intake of micronutrients, protein, and energy) among pregnant women and early breastfeeding practices (early initiation of and exclusive breastfeeding) be improved by the nutrition-focused SBCC interventions?
- 4) What are the **barriers and opportunities** for completing 8 ANC contacts?

1.3 Trial design

The present study is designed as a two-arm cluster-randomized, non-masked trial, consisting of two cross-sectional surveys at baseline and endline. The unit of randomization is the health and social promotion center (CSPS) catchment area. The study is designed to have sufficient power to estimate differences between study groups across regions (**Figure 1**). A baseline cluster/facility-level and household survey will take place in November-December 2019. As soon as the baseline survey is completed, the intervention will be implemented at the CSPS and in the villages of the intervention group for up to 12 months. The endline survey will take place approximately one year later in January-February 2021. The repeated cross-sectional study design will allow us to assess the impact of the maternal nutrition interventions on currently pregnant and recently delivered women.

Figure 1. Trial flow

[figure not shown]
Note: CSPS: Centre de Santé et de Promotion Social. The baseline and endline surveys will include cross-sectional interviews of pregnant, and recently delivered women and their husbands, as well as providers of ANC services.

II. Methods: Participants, Interventions and Outcomes

2.1 Study setting

The study will be conducted in Boucle du Mouhoun and Hauts-Bassins, two of the 13 regions of Burkina Faso (**Figure 2**), often referred to as the country's breadbasket. Their capital cities are located 273 km and 360 km respectively, from Ouagadougou (the capital of the country). The regions were selected with the Government of Burkina Faso based on regional-level engagement and ownership, presence of community health workers and functioning community-women's groups known as Groupes d'Apprentissage et de Suivi des Pratiques Optimales d'Alimentation du Nourrisson et du Jeune Enfant (GASPA), size of the region, ANC attendance and security concerns.

Figure 1: Study regions

In Burkina Faso, the health care system is organized into three administrative levels: central, intermediate and peripheral [10]. Health facilities are also organized in three levels as follows: the first level known as health district includes medical centers with surgical services (CMA), health and social promotion centers (CSPS) and isolated maternity units; the second level with regional hospitals (CHR); and the third level includes university/national hospitals (CHU). At the district level, CMA represents the referral center for health centers of the first level. In Boucle du Mouhoun, two out of six health districts and two out of eight in Hauts-Bassin were selected as part of the study.

ANC coverage with at least one ANC visit is very high in Burkina Faso. About 97% of recently-pregnant women reported attending ANC at least once during their last pregnancy in 2017 [13]. The majority of women who received ANC also received it from a skilled provider, mostly from a midwife (71.3% in Boucle du Mouhoun, 85.8% in Hauts-Bassins) or nurse (19.1% in Boucle du Mouhoun, 17.9% in Hauts-Bassins) [13]. Most women attended ANC at least twice during their pregnancy, and roughly one-third of women in Boucle du Mouhoun and half of women in Hauts-Bassins are within their first trimester at the time of their first ANC visit. At national and regional levels, approximately one-third of women attended at least four ANC visits (as recommended until 2016) during pregnancy [12].

IFA consumption is nearly universal in Burkina Faso [13]. Current WHO guidelines recommend daily IFA supplementation (30-60 mg elemental iron and 400 mcg folic acid) for women during pregnancy,

beginning as early as possible to prevent maternal anemia, puerperal sepsis, low birth weight, preterm birth, maternal anemia and iron deficiency [14]. Ideally, pregnant women should receive IFA tablets no later than the first trimester, corresponding to 6 months (180 days) of supplementation. Ninety-seven percent of women in Boucle du Mouhoun and Hauts-Bassins reported taking at least one IFA or iron tablet during their most recent pregnancy, with 70.6% and 86.0% of women taking at least 90 tablets, respectively [13].

According to the 2017 PMA2020 nutrition survey, calcium supplementation is not common [13]. WHO currently recommends daily calcium supplementation (1.5-2.0 g oral elemental calcium) in populations with low dietary calcium intake to reduce the risk of pre-eclampsia. However, in Burkina Faso calcium supplementation during pregnancy is not yet recommended until further evidence becomes available.

Women's dietary diversity is poor. The mean dietary diversity score (out of 10 food groups) among recently-pregnant women is 3.9 in both regions, slightly higher than the national average of 3.4 [13]. Health providers are nearly twice as likely to provide women information on the importance of diet quality (such as eating a variety of foods and high iron foods) during pregnancy than the importance of quantity (i.e. eating extra food) during ANC services [13].

ANC services are provided in nearly all health facilities, and ANC services are offered, on average, 5-6 days per week [11]. Weighing, nutrition counseling, and IFA supplementation are routine ANC services. Weight gain monitoring during pregnancy is important as body mass index and gestational weight gain are indicators of maternal nutrition and are associated with pregnancy outcomes. Among women who attended ANC during their most recent pregnancy during the past two years, nearly all of them were weighed at least once. However, among them, only 62% of women reported receiving information about their weight gain. This proportion was 72.7% in Hauts-Bassin, higher than in Boucle du Mouhoun. [13]. Roughly half of all facilities support community health workers to provide nutrition services.

Breastfeeding is a common practice: in 2017, 97.4% of Burkinabe women have ever breastfed [13]. Early initiation breastfeeding (within one hour) was 60.2 % in Boucle du Mouhoun and 60.3 % in Hauts-Bassins. About 91% and 74% of women reported receiving information on breastfeeding immediately after birth in Boucle du Mouhoun and Hauts-Bassins, respectively. Among those who received information about breastfeeding their newborn, 59% reported breastfeeding within one hour of birth, and 55% of women reported exclusively breastfeeding their baby.

In the two health districts in Boucle du Mouhoun and two in Hauts-Bassin selected as potential intervention areas, an exhaustive list of all CSPA was prepared (total of 223 CSPA in Boucle du Mouhoun and 182 CSPA in Hauts-Bassins). Areas with high security risk, physical inaccessibility, and presence of similar intervention programs were excluded from the study. The final list of 80 CSPA catchment areas included in the study is provided in **Appendix 1**.

2.2 Eligibility criteria

The study includes two main samples: pregnant women (PW) and recently delivered women (RDW), to assess diet during pregnancy (among PW) and intervention exposure throughout pregnancy (among RDW).

Inclusion criteria:

- 1) Women of reproductive age (15 to 49 years old)

- 2) Currently pregnant or having a living child under 6 months of age (recently delivered) at the time of the survey
- 3) Residency in the health center catchment area
- 4) Informed consent

Exclusion criteria:

- 1) Severe illness (e.g., any severe illness symptoms mentioned/identified by the woman, a relative or the enumerator) in woman and/or child requiring immediate hospital referral
- 2) Chronic or congenital illness (e.g., any health condition mentioned/identified by the woman, a relative or the enumerator) in women and/or child interfering with dietary intake

At the health center level, health staff particularly the nurse-midwife responsible for providing ANC, and community health workers are eligible to participate in one-to-one interviews after providing informed consent.

2.3 Interventions

The package of maternal nutrition interventions will include intensified counseling on diet quality during pregnancy, distribution of and counseling on IFA supplements for better adherence, counseling on early initiation of and exclusive breastfeeding, weight-gain monitoring, systems strengthening through training and supportive supervision, as well as community mobilization. Intervention components are presented in **Table 1**.

Table 1: Description of interventions for intervention and control areas

CORE INTERVENTIONS	INTERVENTION AREAS	CONTROL AREAS
HEALTH FACILITY LEVEL:		
Counseling on diet quality	
 • Intensified counseling on dietary diversity and quality using job aids 	
 • Standard nutrition counseling
Distribution and promotion of IFA supplementation	
 • Intensified counseling on purpose of IFA supplements, managing side effects, and importance on adherence to daily consumption • Distribution/prescription of sufficient IFA supplements at each ANC visit/contact • Use of reminders for women and their spouses • Monthly stock monitoring to assure sufficient supplies 	
 • Standard counseling on consumption of IFA and how to manage side effects • Distribution/prescription of IFA at each ANC visit • Routine stock monitoring
Weight-gain monitoring	
 • Measurement of weight gain during each ANC visit and advise on healthy weight gain • Use of monitoring sheets 	
 • Standard weight measurement
Counseling on early breastfeeding practices	
 • Intensified counseling on early initiation of breastfeeding and exclusive breastfeeding using job aids 	
 • Standard breastfeeding counseling

Reminders on ANC attendance	
 Reminder on importance of early ANC attendance and 8 visits/contacts (at least 4 visits at health facility) 	
 Standard reminder
COMMUNITY LEVEL:		
Community mobilization	
 Orientation sessions for community leaders (traditional and religious leaders, local associations, etc.) about ANC Gatherings among mothers-in-law, husbands, and other influencers about ANC and their roles Promotion of ANC service utilisation and the importance of early ANC visit during the first trimester. Identification of pregnant women for early ANC 	
 Standard ASBC activities
Interpersonal communication in GASPA (women's groups) and during home visits	
 Focused discussions during GASPA meetings 2-3 home visits per pregnant woman by ASBCs (Counseling on diet quality, breastfeeding, importance on adherence to daily IFA consumption and side effect management, etc.) 	
 Standard GASPA meetings Standard ASBC activities
SYSTEM SUPPORTS:		
Training/refreshers	
 Training on nutrition interventions during ANC for all ANC providers and community health workers 	
 Standard government training
Supervision	
 Semi-annual supervision by DRS Quarterly supportive supervision of health facility staff by the health district management team Monthly supportive supervision of ASBC 	
 Quarterly integrated supervision for all care providers Standard supervision of ASBC every 2 months
Progress review	
 Monthly review between health facilities and ASBC 	
 None
Data recording and monitoring	
 Training and recording of up to 8 ANC visits and nutrition services on registers Training on data utilization to improve service coverage and quality 	
 Routine data recording and monitoring

2.4 Outcomes

The primary outcome indicators of the study are focused on diet quality and IFA supplementation. These include:

- 1) **Maternal dietary diversity among pregnant women**
 - i. Mean number of food groups consumed by pregnant women
- 2) **Use of iron-folic acid (IFA) supplements among RDW**
 - i. Mean number of IFA tablets consumed during pregnancy

The secondary outcomes relate to exposure to and utilization of key maternal nutrition, weight gain monitoring, and early breastfeeding interventions, as well as health worker knowledge and capacities at the points of service delivery. These include:

- 3) Maternal diet quality: proportion of pregnant women who achieve minimum dietary diversity; and micronutrient, protein and energy adequacy among pregnant women compared to the recommended dietary intake
- 4) Proportion of women who received 90+ IFA supplements during pregnancy
- 5) Early initiation of breastfeeding and exclusive breastfeeding practices of children
- 6) Use of ANC services (total number of ANC visits/contacts at facility and community levels and timing of the first ANC visit)
- 7) Exposure to nutrition interventions during ANC, including weight gain monitoring (proportion of women who are weighed and counselled about adequate weight gain, total number of times women are weighed during pregnancy)
- 8) Exposure to nutrition information from community health workers (proportion of women who were visited at home during pregnancy, total number of times visited), community groups, and other sources
- 9) Health worker knowledge on benefits and service provision for IFA supplementation, dietary diversity counselling, weight gain monitoring, and breastfeeding counselling
- 10) Availability of service supports (IFA supplies, records/registers, weight measurement equipment, counseling materials, and training and supervision for health workers)

2.5 Sample size

The two main samples for the primary outcomes are: 1) pregnant women (PW) as this sample allows the assessment of diet quality during pregnancy; and 2) recently delivered women (RDW) who have children under 6 months of age, as this sample provides the best opportunity to assess the primary outcome related to intervention exposure throughout pregnancy (i.e., IFA consumption). Based on an initial mean dietary diversity score of 3.52 food groups across both regions and intra-cluster correlation of 0.110 from the 2019 baseline data (Kim et al., 2020), a significance level of 5% and power of 80%, the sample size of 480 PW per arm is estimated to detect a difference of 0.37 in the mean dietary diversity score after intervention.

For RDW, using an initial mean of 108.64 IFA tablets consumed across both regions and intra-cluster correction of 0.206 at baseline (Kim et al., 2020) and the same assumptions above for statistical significance, the sample size of 960 RDW per arm is estimated to detect a difference of 15 tablets in the mean IFA tablets consumed after intervention. If husbands of RDW are present at the time of the survey, they will also be interviewed briefly about their health and nutrition knowledge and any support provided during pregnancy. Approximately half of the expected sample size of husbands was available at baseline.

Outside of these two main samples, nurses-midwives (1 per CSPA) and community health workers (within 3 villages per CSPA) will be interviewed. In addition, direct observations of ANC visits (2 per CSPA) to assess service quality, followed by exit interviews to assess client satisfaction, will be conducted among a subgroup of pregnant women attending ANC at the time of survey.

The overall study samples sizes are presented in **Table 2**.

Table 2: Estimated sample sizes

	Baseline 2019		Endline 2020	
	Intervention	Control	Intervention	Control
Pregnant women	480	480	480	480
Women with children 0-5 months old	960	960	960	960
Husbands of women with children 0-5 months old	960	960	960	960
Nurses-midwives	40	40	40	40
Community health worker (ASBCs)	120	120	120	120
ANC observation & exit interview	80	80	80	80
Total	2,640	2,640	2,640	2,640

2.6 Recruitment

In the catchment area of the pre-selected CSPA, a census will be conducted in three randomly selected villages representing the CSPA catchment area to identify PW and RDW. From two separate lists (for PW and RDW), women will be randomly selected by simple random sampling until the required sample sizes are reached. At least 10 and 24 households per cluster need to be visited in the villages to identify PW and RDW, respectively.

At each CSPA, the nurse-midwife mainly responsible for providing ANC services will be invited participate in the study. In each surveyed village, the community health worker (ASBC) mainly responsible for ANC/care for pregnant women or, in the case that more than one ASBC is responsible, with the longest duration in that position will be invited to participate in the study. In addition, at each CSPA, two ANC sessions that take place during the time of the survey will be observed, with prior permission and consent for observation and post-observation exit interview.

III. Methods: Assignment of interventions

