### 1.2 Impact evaluation study design

The impact evaluation of A&T's interventions used a cluster-randomized design with repeated cross-sectional surveys at baseline and endline. We applied stratified random allocation to 80 health centers (CSPS, Centre de Santé et de Promotion Social) within four health districts (Boromo, Toma, Dande, and Lena), which were assigned to either the A&T intervention (40 CSPS) or control areas (40 CSPS). The baseline survey was conducted in November-December 2019 and the endline survey was conducted in January-March 2021 in the same 80 CSPS catchment areas, thereby creating panel data at the CSPS level (not at individual level). Program implementation duration was approximately 12 months, with a couple of months of interruption due to the COVID-19 pandemic in March-April 2020.

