### 1.3 Study sample

The two main study sample groups are: 1) pregnant women (PW), as this sample allows the assessment of dietary diversity and adequacy of micronutrient, protein and energy intake during pregnancy; and 2) recently delivered women (RDW) who have children less than 6 months of age, as this sample provides the best opportunity to assess the primary outcomes related to intervention exposure throughout pregnancy. PW and RDW were sampled separately but within the same CSPS catchment areas. For PW, we estimated a total sample size of 960 women (480 per arm) to detect a difference of 0.37 food groups in the mean dietary diversity score. For RDW, we estimated a total sample of 1920 women (960 per arm) to detect a difference of 15 tablets in the mean IFA tablets consumed after intervention.

Additionally, we included all husbands of RDW present at the time of the survey. Outside of the two main sample groups, nurses-midwives (N-M, 1 per CSPS) and community health workers (ASBC, within

1-3 villages per CSPS) were interviewed. Direct observations of ANC visits (2 per CSPS) to assess service quality, followed by exit interviews to assess service recall and client satisfaction, were conducted among pregnant women attending ANC at the time of the survey.

Table 1: Sample sizes

		Baseline 2019		Endline 2020	
Survey respondent type		Intervention	Control	Intervention	Control
Household survey:					
1	Pregnant women + 24h dietary recall	480	480	480	480
2	Recently delivered women with children <6 months	960	960	960	960
3	Husbands of RDW with children <6 months	960	960	960	960
Service provider survey:					
4	Nurses-midwives	40	40	40	40
5	Community health worker (ASBCs)	120	120	120	120
Observations:					
6	ANC observation + exit interview	80	80	80	80
Total:		2,640	2,640	2,640	2,640

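### Does the Protocol's recruitment floor of 10 households per cluster undercut the planned 480 pregnant women per arm?

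*Protocol*

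**What the plan says.** Protocol 2.5 sets the target for the first primary outcome: "the sample size of 480 PW per arm is estimated to detect a difference of 0.37 in the mean dietary diversity score after intervention". For the second it states that "the sample size of 960 RDW per arm is estimated to detect a difference of 15 tablets in the mean IFA tablets consumed after intervention". Protocol Table 2, SAP 1.3 and SAP Table 1 repeat 480 PW and 960 RDW per arm at each survey. Protocol 2.1 counts 80 catchment areas in the study, and SAP 1.2 splits them 40 and 40.

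Protocol 2.6 describes how women are found. A census is taken in three randomly chosen villages per catchment area, separate lists of PW and RDW are drawn up, and then "women will be randomly selected by simple random sampling until the required sample sizes are reached". The next sentence adds the field minimum: "At least 10 and 24 households per cluster need to be visited in the villages to identify PW and RDW, respectively".

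For the provider samples, Protocol 2.5 states that "nurses-midwives (1 per CSPA) and community health workers (within 3 villages per CSPA) will be interviewed", and it plans two observed antenatal visits per centre.

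**The concern.** The Protocol's other per-centre figures multiply exactly to their rows in Table 2. The pregnant-women figure does not, and it is the only per-cluster number for that sample in either document. The same sentence applies the same minimum wording to both groups, yet the RDW number equals its planned average exactly while the PW number sits two below. That pattern suggests an error rather than a deliberate floor.

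The sample matters because it carries dietary diversity, a primary outcome. A field team working centre by centre and treating 10 as its quota would finish with 400 women per arm, one sixth fewer than planned, and with less power than the 80% the Protocol claims.

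**Working it through.** **Inputs.** 40 CSPS per arm (SAP 1.2). Per-centre figures from Protocol 2.5 and 2.6. Targets per arm from Protocol Table 2. For the consequence: intra-cluster correlation (ICC) 0.110, difference 0.37, 5% significance and 80% power (Protocol 2.5), two-sided testing (SAP 3.1).

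**Step 1: per-centre figure × 40 against Table 2.**

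| Sample | Per centre | × 40 | Table 2 | Agrees |
|---|---|---|---|---|
| RDW | 24 | 960 | 960 | yes |
| Nurse-midwives | 1 | 40 | 40 | yes |
| Community health workers | 3 | 120 | 120 | yes |
| Antenatal observations | 2 | 80 | 80 | yes |
| PW | 10 | 400 | 480 | no |

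The planned average is 480 / 40 = 12 PW per centre. The gap is 480 − 400 = 80 per arm, or 80 / 480 = 16.7%. Husbands have no per-centre figure to check.

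**Step 2: are the two statements incompatible?** Table 2 gives a total of women per arm. Protocol 2.6 gives a lower bound on households visited per cluster. An average of 12 women per cluster satisfies a floor of 10 households if more than 10 are visited, or if some households hold more than one pregnant woman. The documents give no number of pregnant women per household and do not require equal numbers per cluster. The stopping rule in the preceding sentence refers to the required sample size, which the documents state only as 480 per arm. No passage plans 400.

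**Step 3: what if 10 had been the quota, one woman per household?** The Protocol states neither the standard deviation (SD) nor its formula, so its 480 cannot be reproduced independently. I take 80% power at 480 as given, assume equal clusters and use design effect = 1 + (m − 1) × ICC.

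- At m = 12: 1 + 11 × 0.110 = 2.21; effective size 480 / 2.21 = 217.2 per arm. Solving 0.37 = (1.960 + 0.842) × SD × √(2 / 217.2) gives an implied SD of 1.376.
- At m = 10: 1 + 9 × 0.110 = 1.99; effective size 400 / 1.99 = 201.0 per arm, 7.5% lower.
- Ratio of standard errors: √(217.2 / 201.0) = 1.0395.
- Detectable difference: 0.37 × 1.0395 = 0.385.
- Power at 0.37: Φ(2.802 / 1.0395 − 1.960) = 76.9%.

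If the SD is instead assumed to lie between 1.2 and 1.5, power is 87.1% to 69.6% at 10 per cluster, against 89.5% to 72.9% at 12. The difference between the two cluster sizes is 2 to 3 percentage points throughout. The loss is modest because the women given up are partly redundant within clusters.

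**The case for a change.** The best argument for acting is that the minimum wording cannot explain the 10, because the same wording accompanies a 24 that equals the RDW average exactly. A genuine safety floor would be expected to sit below the average for both groups. The required number per cluster is written nowhere else, so a supervisor would have only the 10 to work from, and correcting one number costs almost nothing. A more pessimistic calculation is also available: if the difference-in-difference analysis removed fully persistent cluster effects, the standard-error ratio would be √(12 / 10) = 1.0954 and power at 10 per cluster about 72.5%.

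The evidence for a slip stands, and I would read it as one. The rest does not carry the point further. The total target is clear once 2.6 is read with 2.5 immediately before it, and 12 follows from one division. The 72.5% needs two conditions that the documents do not state: a quota of 10, and cluster effects that persist completely between surveys. Editing 2.6 now would not alter the fieldwork either: SAP 1.2 describes the baseline survey as done and reports that "the endline survey was conducted in January-March 2021 in the same 80 CSPS catchment areas". The numbers achieved are what would show a shortfall, and SAP 3.1 already provides a flow diagram of clusters and individuals. Its figure is not reproduced in the text available, so its level of detail cannot be judged.

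**Conclusion.** The mismatch is real and clerical: a floor of 10 households stands where the planned average is 12 women per cluster, and the Protocol does not explain it. It does not contradict the planned sample, because it is a minimum, it counts a different unit, and it is governed by the rule to keep sampling until the required size is reached. The 480 per arm, the 0.37 detectable difference and the analysis are unchanged, so no change to the plan follows.

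The conditional loss, about 3 points of power and a detectable difference of 0.385, rests on a quota of 10 with one woman per household, on equal clusters, and on the Protocol's own 80% at 480. It should not be claimed as an effect of the plan. It would become relevant only if the achieved numbers showed about 10 PW per cluster.
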